	All medications a subject receives from the signing of informed consent through the 28-Day Follow-Up visit will be documented.
	 CYP3A4 inhibitors/inducers should be used with caution. Subjects on concomitant medication known to have potential for QTc prolongation will be excluded.
Safety Evaluation	Safety data will be collected from the time the subject signs the informed consent form until 28 days after their last dose of study drug (the adverse event [AE] reporting period). The primary safety outcome will be the percentage of subjects experiencing treatment-emergent AEs (TEAEs) in each group.
	Safety assessments will include AEs, serious adverse events (SAEs), PEs, vital sign measurements (blood pressure, pulse rate, respiratory rate, and temperature), clinical laboratory evaluations (hematology, chemistry and urinalysis), and electrocardiograms (ECGs). Reasons for treatment discontinuation because of toxicity will be documented.
	As this is the first study of belumosudil in subjects with dcSSc, careful monitoring of all toxicities will be carried out.
Efficacy/Activity	Primary Efficacy Endpoint
Evaluation	The primary efficacy endpoint is the effect of belumosudil compared to placebo for CRISS, an exponential algorithm determining the predicted probability of improvement from baseline, incorporating changes in mRSS, FVC % predicted, and physician and patient global assessments. The outcome is a continuous variable between 0.0 and 1.0 (0-100%). A higher score indicates greater probability of improvement. A CRISS score ≥ 20% is considered a clinically meaningful improvement.
	Secondary Efficacy Endpoints
	Secondary efficacy outcomes include the change from baseline in mRSS, FVC, SHAQ-DI, physician global assessment, and patient global assessment for belumosudil-treated and placebo-treated subjects.
	Onset/progression of ILD will be evaluated by the effect of belumosudil compared to placebo in the change in predicted FVC
	In addition, changes in lung fibrosis on HRCT performed at baseline, Week 24 and Week 52 will be assessed only in subjects who have SSc lung disease at screening.
	Exploratory Endpoints
	Exploratory outcome assessments include changes in PD parameters measured in plasma and/or skin biopsy sample (discussed below).
Pharmacokinetics	Sparse PK sampling will be performed on Weeks 4 and 8 (i.e., Days 29 and 57) immediately prior to belumosudil dosing and 3 hours post-dose

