Pharmacodynamics	All subjects will have PD blood samples drawn at the following time points prior to dosing: Week 1 (Day 1, baseline), Week 8 (Day 57), Week 24 (Day 169), and Week 52 (Day 365). These samples will be

analyzed to evaluate autoantibody levels at baseline and biomarkers of extracellular matrix turnover which could correlate with both SSc disease activity and disease modification by belumosudil.

All subjects will be required to provide skin biopsies obtained from the dorsal mid-forearm at the Week 1 (Day 1) and Week 24 (Day 169) visits. An optional skin biopsy may be obtained at the Week 52 (Day 365) visit. Biopsy sections will be assessed for histology including fibrosis and inflammation. In addition, gene expression profiling will be performed on skin biopsies.

Statistical Analysis

This proof of concept study will inform future development of belumosudil in dcSSc. The sample size is not driven by hypothesis testing. Two populations will be employed in the analysis of study data:

- The Modified Intent-to-Treat Population (mITT) will consist of all subjects who receive at least one dose of study drug.
- The Evaluable for Efficacy/Activity population will consist of subjects who have received at least 80% of expected study drug and have post-baseline efficacy data.

The primary endpoint will be analyzed on the mITT Population.

Demographics, subject disposition, and baseline characteristics will be summarized in each population and by group.

Efficacy will be evaluated by comparing Week 24 CRISS scores for subjects treated with belumosudil and placebo. Secondary endpoints will include changes in mRSS, FVC, SHAQ-DI, Physician Global Assessment, and Patient Global Assessment from baseline to Week 24 in subjects treated with belumosudil compared to placebo and the change from baseline for subjects with belumosudil at Week 52. No formal comparison will be conducted between the belumosudil QD and belumosudil BID dosing cohorts.

Treatment-emergent AEs will be evaluated using the Common Terminology Criteria for Adverse Events (CTCAE) v 5.0. The total sample size of 20 subjects per belumosudil dose group will provide > 90% probability of one or more belumosudil subjects experiencing an AE that has an underlying rate of $\geq 14\%$ and > 80% probability of one or more subjects in the study experiencing an AE that has an underlying rate of $\geq 10\%$.

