6. EFFICACY AND SAFETY ASSESSMENTS

6.1 EFFICACY ENDPOINTS

Efficacy measurements will be performed as outlined in Appendix A.

The primary efficacy endpoint is the effect of belumosudil compared to placebo for the CRISS at the end of Week 24 in the mITT Population. The CRISS exponential algorithm determines the predicted probability of improvement from baseline, incorporating changes in mRSS, FVC% predicted, and Physician and Patient Global Assessments. The outcome is a continuous variable between 0.0 and 1.0 (0-100%). A higher score indicates greater probability of improvement. A CRISS score \geq 20% is considered a clinically meaningful improvement.

Other efficacy outcomes include the change from baseline in mRSS for belumosudil-treated and placebo-treated subjects. The mRSS is a measure of skin thickness rated with scores ranging from 0 (normal) to 3 (severe skin thickening) across 17 different sites. The total score is the sum of the individual skin scores in the 17 body areas (i.e., face, hands, fingers; proximal area of the arms, distal area of the arms, thorax, abdomen; proximal area of the legs, and distal area of the legs, feet), giving a range of 0-51 units. The mRSS has been validated for patients with SSc. A negative change from baseline demonstrates improvement.

The effect of belumosudil compared to placebo will be explored for the change in baseline for SHAQ-DI, which assesses 5 scleroderma-specific Visual Analog Scale (VAS) items to explore the impact of participant's disease. Each VAS item will be rated separately in scale of a 0–100 mm, with higher scores indicating more severe disease. The 5 items are: (1) intestinal disease, (2) breathing problem, (3) Raynaud syndrome, (4) finger ulcers, and (5) overall disease.

Onset/progression of ILD will be evaluated by the effect of belumosudil compared to placebo in the change in predicted FVC, which is based on institutional standards and will be measured as part of PFTs, including FEV₁, FVC, DL_{CO}, and total lung capacity (TLC). The same equipment and tester should be used during the course of the study to the extent possible. The person responsible for conducting the PFTs will be required to comply with the study guidelines and the American Thoracic Society/European Respiratory Society joint criteria on lung function testing.

Confidential and Proprietary

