9.8.1 Primary Efficacy Endpoint

The primary efficacy endpoint of this study is to evaluate the efficacy of belumosudil compared to placebo for the CRISS score at Week 24

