9.8.4 Analysis Method

- Mixed models with treatment and week as fixed effects, and subject as random effect will be used to analyze all longitudinal efficacy endpoints.
- Descriptive statistics will be provided for all endpoints by treatment groups and visits.

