2.2 Study Design

KD025-209 is a Phase 2, placebo-controlled, double-blinded, randomized, multicenter trial in subjects with dcSSc with an open-label extension. The study schematic is shown below in Figure 1.

Subjects who have signed an Institutional Review Board (IRB)/ Independent Ethics Committee (IEC)-approved informed consent form and met all of the inclusion and do not meet all of the exclusion criteria will be enrolled. A total of 60 subjects will be randomized into 3 groups (1:1:1) to receive orally administered belumosudil 200 mg QD (n = 20), belumosudil 200 mg BID (n = 20), or matched placebo (n = 20) for 28 weeks. The study will be double-blinded for the first 28 weeks followed by an open-label extension of 24 weeks. After unblinding, the subjects in Group 1 and 2 will continue on the same belumosudil dose whereas the subjects in the placebo group will be re-randomized to one of the belumosudil doses (200 mg QD or 200 BID) in 1:1 fashion.

Efficacy will be assessed throughout the 52-week dosing period using CRISS, mRSS, PFTs, physician global assessment, SHAQ-DI.

[figure not shown]

Figure 1 KD025-209 Study Schema

be on a stable dose for at least 6 months prior to screening

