3.8 Definition of Efficacy Endpoints

3.8.1 Primary Efficacy Endpoint: CRISS

The primary efficacy endpoint is Combined Response Index in Diffuse Cutaneous Systemic Sclerosis (CRISS).

CRISS is a 2-step process for use in a clinical trial.

Step 1: patients who develop new onset of renal crisis, new onset or worsening of lung fibrosis, new onset of pulmonary arterial hypertension, new onset of left ventricular failure during the trial are considered as not improved and assigned a probability of improving equal to 0.0.

Step 2: For the remaining patients, step 2 involves computing the predicted probability of

improving for each individual, using the equation shown below.

$$\frac{\exp\left[-5.54 - 0.81 * \Delta_{MRSS} + 0.21 * \Delta_{FVC\%} - 0.40 * \Delta_{Pt-glob} - 0.44 * \Delta_{MD-glob} - 3.41 * \Delta_{HAQ-DI}\right]}{1 + \exp\left[-5.54 - 0.81 * \Delta_{MRSS} + 0.21 * \Delta_{FVC\%} - 0.40 * \Delta_{Pt-glob} - 0.44 * \Delta_{MD-glob} - 3.41 * \Delta_{HAQ-DI}\right]}$$

where Δ_{MRSS} indicates the change in mRSS from baseline to follow up, $\Delta_{FVC\%}$ denotes the change in FVC% predicted from baseline to follow up, $\Delta_{Pt-glob}$ indicates the change in patient global assessment, $\Delta_{MD-glob}$ denotes the change in physician global assessment, and Δ_{HAQ-DI} is the change in HAQ-DI. All changes are absolute change (Time₂-Time_{baseline}).

As patient global assessment and physician global assessment are based on a VAS of 0 (Extremely Poor)-100 (Excellent) in CRF. When calculating the CRISS score, these 2 scores should be divided by 10 firstly to make it in a 0-10 scale. If any of the component scores are missing, CRISS score will be calculated based on the imputed component score using LOCF method.

The outcome is a continuous variable between 0.0 and 1.0 (0-100%). A higher score indicates greater probability of improvement. A CRISS score ≥ 20% is considered as the minimal detectable difference and will be described as CRISS20 in the SAP. A CRISS score >= 60% is considered as the minimally important difference and will be described as CRISS60 in the SAP. This will be the primary variable for efficacy.

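### SAP 3.8.1 most naturally makes CRISS60 the primary variable where the protocol has the continuous Week 24 CRISS score; it fixes no main analysis, and its Wald method fails if an arm has no responders

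*SAP*

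**What the plan says.** **Protocol.** Section 9.8.1 reads: "The primary efficacy endpoint of this study is to evaluate the efficacy of belumosudil compared to placebo for the CRISS score at Week 24". Section 6.1 and the Synopsis describe that score as continuous from 0 to 1 and give a single threshold: "A CRISS score ≥ 20% is considered a clinically meaningful improvement". No 60% threshold appears. The Synopsis adds: "Efficacy will be evaluated by comparing Week 24 CRISS scores for subjects treated with belumosudil and placebo". On method, section 9.8.4 says: "Mixed models with treatment and week as fixed effects, and subject as random effect will be used to analyze all longitudinal efficacy endpoints".

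**SAP, variable.** Section 2.1.1 puts the primary objective at Week 24 in the mITT population. Section 3.8.1 also calls the score continuous, but describes 20% as the minimal detectable difference. It continues "A CRISS score >= 60% is considered as the minimally important difference and will be described as CRISS60 in the SAP", and the very next sentence is "This will be the primary variable for efficacy".

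**SAP, analyses.** The next part of 3.8.1 speaks of primary endpoints in the plural and lists:

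- a logistic regression of CRISS60, each dose against placebo;
- an MMRM of the continuous score;
- a t-test, replaced by Wilcoxon-Mann-Whitney if the data are not normal.

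Section 3.1.4.4 has a parallel switch from raw to rank-transformed scores in the MMRM. Section 3.1.4.3 gives Clopper-Pearson intervals for each arm's proportion and, for the comparison, an odds ratio with a Wald 95% interval and a p-value from an unnamed test.

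**The concern.** A reader cannot tell from the SAP which single result answers the primary objective. If it is CRISS60, the SAP has changed the protocol's primary variable from a continuous score to a responder rate, at a threshold the protocol does not contain, without saying so. If it is the continuous score, three things remain open: whether the MMRM or the two-sample test leads, whether scores or ranks are analysed, and which groups the two-sample test compares. SAP 2.4 defines a pooled belumosudil group (K) as well as the two dose groups.

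Protocol 9.7.1 says the main focus is guidance for follow-up studies, and 9.7.4 leaves the pre-specified analyses to the SAP. A choice left open there can be made after the data are seen. Separately, the one comparison method given for CRISS60 has no usable result in a case that is possible with 20 patients per arm.

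**Working it through.** The documents give no efficacy power, effect size or expected CRISS60 rate, so there is no planned figure to reproduce. Inputs taken from them are 20 patients per arm (SAP 3.1.3), the CRISS equation and thresholds (SAP 3.8.1) and the methods in SAP 3.1.4.3 and 3.1.4.4.

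**1. Which variable.** The primary-variable sentence directly follows the definition of CRISS60, and the analysis text that comes next starts with CRISS60. SAP 3.1.4.2 also uses CRISS60 as its example of a binary efficacy endpoint. Against that, the paragraph opens with the continuous score, and SAP 2.1.1 and the protocol name CRISS without a cut-off. CRISS60 is the more natural reading, but not the only one.

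**2. How far apart the thresholds are.** logit(0.60) − logit(0.20) = 0.405 − (−1.386) = 1.79. With the other components unchanged, that is 1.79/0.81 = 2.2 mRSS points or 1.79/3.41 = 0.53 HAQ-DI units. For a patient with no Step 1 event in whom only mRSS changes, the linear predictor is −5.54 + 0.81 × (fall in mRSS):

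- fall of 5: −1.49, score 0.18
- fall of 6: −0.68, score 0.34
- fall of 7: 0.13, score 0.53
- fall of 8: 0.94, score 0.72

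A fall of 6 or 7 points passes 20% and fails 60%, so the two documents classify such a patient differently.

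**3. Normality.** A patient with no change scores exp(−5.54)/(1 + exp(−5.54)) = 0.004, and Step 1 patients score exactly 0. A bounded score with a mass near zero is therefore foreseeable at the design stage. The SAP gives no test, cut-off, visit or object (scores or residuals, by arm or pooled) for the check. To see whether the rule matters, 8,000 two-arm trials of 20 per arm with no effect were simulated for each of five ASSUMED logit-normal score distributions (median logit −3 to 0, SD 3 to 5). Shapiro-Wilk at 5% on pooled residuals rejected in 98% to 100% of trials. A rule of absolute skewness above 1 rejected in 0.2% to 64%. The unstated rule can decide which analysis is run.

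**4. No responders in an arm.** P(0/20) = (1 − p)^20, with p an ASSUMED true rate:

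| p | one given arm | at least one of three arms, same p |
|---|---|---|
| 5% | 0.95^20 = 35.8% | 1 − (1 − 0.358)^3 = 73.6% |
| 10% | 0.90^20 = 12.2% | 1 − (1 − 0.122)^3 = 32.2% |
| 20% | 0.80^20 = 1.2% | 1 − (1 − 0.0115)^3 = 3.4% |

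If the empty arm is placebo, both dose comparisons fail. For 0/20 against 10/20 the maximum-likelihood odds ratio is infinite. A fit stopped at 25 iterations shows a log odds ratio of about 23.6 with standard error about 17,768, hence Wald p = 0.999. Fisher's exact p is 0.0004 and the likelihood-ratio p is 0.00003. The Firth estimate (0.5 added to each cell) is (10.5 × 20.5)/(10.5 × 0.5) = 41, Wald-form 95% interval 2.2 to 770.

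The replacement also has to be named. For 0/20 against 6/20, Fisher's p is 0.020 and the likelihood-ratio p is 0.002. The Firth odds ratio is (6.5 × 20.5)/(14.5 × 0.5) = 18.4, with a Wald-form interval of 0.96 to 353. The risk difference is 30 points (Newcombe score 95% interval 7.7 to 51.9).

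**The case against.** The strongest defence is that the study is exploratory: Protocol 9.7.2 and SAP 3.1.3 say that neither sample size nor power is driven by hypothesis testing. That stands. A reader might infer that several unranked tests produce a false confirmatory claim, but the documents make no such claim and set no success criterion.

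Other replies stand in part:

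- CRISS60 is the likelier meaning, so the text is less ambiguous than it looks. Accepted; but the main defect is then an unrecorded conflict with the protocol.
- A reader might infer that no continuous analysis has a stated comparison. The MMRM code in SAP 3.1.4.4 requests differences from a control, and Protocol 9.7.1 sets each dose beside placebo. Only the t-test/Wilcoxon groups are unnamed.
- Under Shapiro-Wilk the switch would nearly always lead to ranks. True under the assumed distributions, but the SAP does not name Shapiro-Wilk.
- An empty arm is unlikely at rates of 20% or more, and the within-arm Clopper-Pearson intervals (0/20: 0 to 16.8%) and the continuous analyses are unaffected. Accepted.

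Two stronger readings are tempting. First, the MMRM uses visits to Week 52, and after Week 28 "the subjects in the placebo group will be re-randomized to one of the belumosudil doses", so open-label data might seem to contaminate the Week 24 result. The documents do not support this: the model has treatment-by-visit terms, unstructured covariance as first choice and estimates by visit, and SAP 3.1.1 defines a separate Week 0 to 24 analysis. Second, the Wilcoxon test might seem the demonstrably better choice. Its simulated power relative to CRISS60 depends on the assumed effect: a uniform shift on the logit scale favours Wilcoxon, while a large gain in a minority of patients can reverse the order. The documents do not say which to expect, so power is not used here to choose a test.

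**Conclusion.** The point holds and should be fixed before unblinded results are analysed. On the text alone, the SAP's primary variable most naturally differs from the protocol's, the 20% threshold carries two meanings, no main analysis is named, and a data-dependent switch has no rule. These findings need no assumption. The score gap (2.2 mRSS points between thresholds) and the 0.004 for no change follow directly from the SAP equation.

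The zero-responder problem is conditional: a 36% or 12% chance per arm at true CRISS60 rates of 5% or 10%, and about 1% at 20%. Those rates are assumptions, and so are the distributions behind the normality comparison. The consequence is a headline result that is unclear or open to selection in a study meant to guide later ones. It is not a wrong sample size or a false confirmatory finding.

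**What to change.** 1. **SAP 3.8.1, variable.** Replace the pronoun with one named Week 24 variable, each dose against placebo, mITT. The default is the protocol's continuous CRISS score, with CRISS20 and CRISS60 as supportive responder analyses. If the sponsor intends CRISS60, say so and record it as a change from the protocol. Give the 20% threshold one meaning in both documents.
2. **SAP 3.8.1 and 3.1.4.4, main analysis.** Delete the normality switch and fix one main Week 24 analysis in advance. Either use the Protocol 9.8.4 mixed model with a Week 24 contrast and keep Wilcoxon as sensitivity, or use Wilcoxon with a Hodges-Lehmann difference and 95% interval, recorded as a departure from Protocol 9.8.4. The second option should state its reliance on the single imputation in SAP 3.1.7.1. Name the groups compared.
3. **SAP 3.1.4.3, CRISS60 comparison.** Use Firth-penalised or exact logistic regression, or Fisher's exact test with a score interval for the risk difference. Name the test behind the p-value and the type of interval.

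The cost is a few sentences and standard SAS options, with no new data. Exact p-values are slightly conservative. If Wilcoxon is chosen, the Hodges-Lehmann difference can be small when many scores lie near zero, so the responder proportions should stand beside it.

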3.1.7.1 Imputation for CRISS Score

Linearization and last observation carried forward (LOCF) method will be used when calculating the primary endpoint CRISS if any of the component scores is missing.

The linearization method will be used when there is a missing observation followed by a non missing observation. The missing value will then be imputed as the average of the previous non missing observation and the next non missing observation. If there is no next non missing observation in the current treatment group then just the last observation will be used.

For patients discontinuing investigational product for any reason, the last non-missing observation before discontinuation will be carried forward to the corresponding endpoint for evaluation. For patients randomized to belumosudil at Week 1, the last non-missing observation in double-blind treatment period will be carried forward to open-label treatment period. For patients randomized to placebo at Week 1, LOCF imputation will be performed within treatment period. The last non-missing observation in double-blind treatment period will not be carried forward to open-label treatment period.

Randomized patients without at least 1 postbaseline observation will not be included for evaluation.

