Analyses of the primary efficacy endpoints will be conducted using the mITT population. The number and percentage of patients achieving CRISS60 response will be summarized by treatment group. Treatment comparisons between each belumosudil dose regimen and placebo in the proportion of patients achieving an CRISS60 response will be analyzed using a logistic regression analysis with treatment in the model.

The continuous CRISS score will be summarized as a continuous endpoint at all post baseline scheduled assessment visits. The continuous CRISS score will be analyzed using the MMRM model, and a t-test comparison. If the data is not normally distributed then the Wilcoxon-Mann-Whitney model will be used instead of a t-test. Missing data will be imputed using the Linearization method The linearization method will take the average of the last observation and the next non missing observation. If there is no next non missing observation in the current treatment group then just the last observation will be used.

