3.8.2 Secondary Efficacy Endpoints

3.8.2.1 mRSS

The mRSS is a measure of skin thickness rated with scores ranging from zero (0; normal) to three (3; severe skin thickening) across 17 different sites. The total score is the sum of the individual skin scores in the 17 body areas (e.g., face, hands, fingers; proximal area of the arms, distal area of the arms, thorax, abdomen; proximal area of the legs, and distal area of the legs, feet), giving a range of 0-51 units. A negative change from baseline demonstrates improvement.

MRSS total score, change from baseline, percent improvement will be summarized as a continuous endpoint at all scheduled assessment visits.

The change from baseline and percent improvement in mRSS total score will be analyzed using the MMRM model. In addition, the change from baseline and percent improvement in mRSS total score will be analyzed using the ANCOVA model. Missing data will not be imputed.

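### Missing CRISS scores are filled by averaging or carry-forward before the continuous-CRISS MMRM, so the Week 24 difference can be biased if scores are still changing and dropout or trajectories differ by arm

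*SAP*

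**What the plan says.** SAP 3.8.1, on the continuous score: "The continuous CRISS score will be analyzed using the MMRM model, and a t-test comparison". A Wilcoxon-Mann-Whitney test replaces the t-test if the data are not normal. The same paragraph then gives the missing-data rule: "Missing data will be imputed using the Linearization method", and "If there is no next non missing observation in the current treatment group then just the last observation will be used".

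SAP 3.1.7.1 gives the detail. For a gap with a later value: "The missing value will then be imputed as the average of the previous non missing observation and the next non missing observation". For dropout: "For patients discontinuing investigational product for any reason, the last non-missing observation before discontinuation will be carried forward to the corresponding endpoint for evaluation". Subjects with no post-baseline observation are left out. SAP 3.8.1 also says, for missing components, that the "CRISS score will be calculated based on the imputed component score using LOCF method"; it does not mention averaging there.

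For mRSS, FVC, both global assessments and SHAQ-DI (SAP 3.8.2.1 to 3.8.2.5) the SAP also plans an MMRM, but with the opposite rule: "Missing data will not be imputed". Protocol 9.8.4 names mixed models for all longitudinal efficacy endpoints and mentions no imputation. No observed-data or other missing-data sensitivity analysis is planned for CRISS.

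**The concern.** An MMRM estimates the Week 24 means from whatever visits were recorded, and this is valid if missingness depends only on observed data. Filling the gaps first removes that property. The model then treats a Week 8 score carried to Week 24 as a Week 24 measurement. If CRISS is still rising, the arm that loses more subjects early is pulled down, whatever the drug does. If the drug raises CRISS faster than placebo, carry-forward shrinks the difference even when dropout is equal.

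The study is exploratory, but Protocol 9.7.1 says its main purpose is to guide later studies. A distorted Week 24 estimate would feed directly into them.

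Unequal dropout is plausible. Protocol 3.9 and 9.6.2 tie stopping to progression and to toxicity, and both can differ by arm. In the earlier placebo-controlled psoriasis study (Protocol 1.4.1.3), completion was 39.1% on 200 mg QD, 27.3% on 200 mg BID and 11.1% on placebo. That is another indication and covers the whole treatment period, so it shows plausibility only. There placebo lost more subjects, so the direction of any bias here cannot be assumed.

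**Working it through.** The plan states no CRISS effect size, SD, trajectory or dropout rate, and SAP 3.1.3 says the sample size is not driven by hypothesis testing. There is therefore no planned figure to reproduce.

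**Step 1: what the MMRM estimates after filling.** The SAP 3.1.4.4 code has treatment, visit and their interaction, with an unstructured covariance. After imputation every analysed subject has a value at each scheduled double-blind CRISS visit. With complete data and a separate mean for each arm and visit, generalised least squares returns the raw arm-by-visit means for any common covariance matrix. The Week 24 contrast equals the plain difference in means of the filled-in scores.

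**Step 2: bias with identical arms and random dropout.** Let e8 and e16 be the excess share of the active arm whose last score is at Week 8 or Week 16, and m8, m16, m24 the common means. Then

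bias (active minus placebo) = -[e8 × (m24 - m8) + e16 × (m24 - m16)].

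Assumptions: means 0.21, 0.35, 0.50, so the rises to Week 24 are 0.29 and 0.15; excess dropout split equally between the two visits. The simulations used 20 per arm, 4000 trials and a logistic-normal CRISS with subject SD 1.8 and residual SD 1.0.

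| Dropout, active vs placebo | Formula | Bias by formula | Simulated, filled-in | 95% interval coverage |
|---|---|---|---|---|
| 20% vs 10% | 0.05×0.29 + 0.05×0.15 | -0.022 | about -0.02 | 94.0% |
| 30% vs 10% | 0.10×0.29 + 0.10×0.15 | -0.044 | -0.042 to -0.045 | 93.2% |
| 40% vs 10% | 0.15×0.29 + 0.15×0.15 | -0.066 | -0.065 | 90% |

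A likelihood fit to the observed scores gave +0.004 at 30% vs 10% and +0.001 at 40% vs 10%.

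**Step 3: other trajectories.** With means 0.10, 0.17, 0.25 and 30% vs 10% dropout: -(0.10×0.15 + 0.10×0.08) = -0.023. The simulation gave -0.022, coverage 94.5%. With flat means the bias is about 0.

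**Step 4: a true effect.** Assume placebo means 0.13, 0.24, 0.35 and active means 0.21, 0.41, 0.57, a Week 24 difference of 0.22. The active arm's rise exceeds placebo's by 0.36 - 0.22 = 0.14 from Week 8 and by 0.16 - 0.11 = 0.05 from Week 16. At 30% dropout in both arms: -(0.15×0.14 + 0.15×0.05) = -0.0285. Simulated results, with dropout either random or concentrated in low scores:

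- 30% vs 30%: -0.028 to -0.033
- 30% vs 10%: -0.064 to -0.069
- 40% vs 10%: -0.094 to -0.099, or 43% to 45% of 0.22
- 10% vs 30% (placebo loses more): about +0.025

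The observed-data fit stayed within 0.003 of the truth throughout.

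**The case against.** Several objections have force.

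- **Which analysis is primary.** SAP 3.8.1 calls CRISS60 or the CRISS score the primary variable in a sentence that follows the CRISS60 definition, and lists the CRISS60 logistic model before the MMRM. A reader might infer that the MMRM is the primary analysis; the text does not settle this. The logistic and t-test/Wilcoxon comparisons are single-visit analyses and do need a rule for missing Week 24 values.
- **CRISS is a composite.** It needs five component changes. A bare no-imputation rule would discard a visit with four of five observed. This stands, and the change must provide for it. It does not justify carrying whole scores forward after discontinuation.
- **False precision.** A reader might infer that the filled-in interval is too narrow. That is not shown: the mean standard error was 0.102 against an actual spread of 0.102 to 0.103, and coverage was 94.7% under equal dropout with no effect. The coverage loss comes from bias.
- **Covariance.** A reader might also infer that repeated values distort the covariance and so the Week 24 result. By Step 1, the covariance does not enter the Week 24 point estimate once the data are complete.
- **Ranks.** SAP 3.1.4.4 switches CRISS to ranks if it is not normal. In the assumed model, Shapiro-Wilk rejected normality in over 80% of trials, so the sizes in CRISS units may not apply to the estimate actually reported. Carry-forward still enters the ranks, but its size there was not calculated.
- **Progression.** The carried-forward score of a subject stopping for progression is near 0: with other changes zero, mRSS +5 gives exp(-5.54 - 4.05) = 0.00007, and FVC -10 points gives 0.0005. Carry-forward then acts as a failure score. This does not extend to toxicity or voluntary withdrawals.
- **Missing-not-at-random dropout.** An observed-data MMRM does not protect against it. The unimputed MMRMs of the CRISS components mitigate the concern only in part.

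**Conclusion.** The concern holds in conditional form. As written, the continuous-CRISS MMRM loses its handling of incomplete data and reports a difference in filled-in means. That difference can be biased when scores are still changing and dropout differs by arm, or when the arms change at different rates.

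It would go too far to say that the Week 24 result will be biased. With no true effect and equal dropout the bias is about 0, and it is near zero with flat scores. At 30% versus 10% dropout the bias of -0.042 is about 0.4 of a standard error (0.042/0.102), so it matters more for the point estimate passed to later studies than for interval coverage. The figures rest on assumed trajectories, variability and dropout. The change should be made: it is cheap, and the SAP already follows the unimputed approach for its secondary scores.

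**What to change.** Revise SAP 3.8.1 and 3.1.7.1 so that they give one consistent rule:

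1. Fit the continuous-CRISS MMRM, or its rank version, to observed CRISS scores, with no carry-forward after discontinuation.
2. Limit component imputation to visits where only some of the five components are missing, and name one method for it.
3. State that Step 1 zeros are kept as observed values from the event onward, and state the estimand this implies.
4. Keep the LOCF/linearised MMRM as a labelled sensitivity analysis.
5. Say which CRISS analysis is primary. The CRISS60 logistic and t-test/Wilcoxon analyses may keep a stated imputation rule.

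The cost is SAP wording and one additional model run. The interval will be somewhat wider if dropout is high; in the simulations the filled-in estimate had a 6% to 9% smaller spread than the observed-data fit.
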